4.2.6.4. Deep Learning Model Selection

To evaluate the performance of the deep learning models, performance metrics including *sensitivity*, *specificity* and *balanced accuracy* will be derived on the test and validation sets (Table 2 and Table 3). The model *AUC-ROC* will be assessed. The final model will be trained on the entire training set to maximize fine tuning, and will finally be tested on the hold-out test set to generate the final performance results.

4.2.6.5. Deep Learning Model Output

The final output of the deep learning approach will be the full set of model predictions for the best-performing model validation, as well as the full set of predictions of the final model on the hold-out test set for the three replications. Both sets of predictions will be paired with their respective labels so that all performance metrics can be calculated.

4.3. Fusion of Classical Machine Learning and Deep Learning Modeling

Methods such as stacking⁵⁴ or bagging²³ may be used to combine the outputs of the classical machine learning and deep learning models. Performance of the combined models will be assessed as detailed in Section 4.2.6.4.

4.4. Well vs. Sick Analysis with Sick State Definition Centered Around Maximum Total Symptom Score

This analysis will investigate the distinction of well and sick states from voice features, with the sick state definition centered around the maximum total symptom score instead of centered around a positive RT-PCR test. For the purpose of this analysis, the sick and well states will be defined as follows:

For participants who have a negative RT-PCR test at swab #1 and a positive RT-PCR test at swab #2:

The **sick state** is defined by considering a window of Electronic Diary data centered around the maximum total symptom score, from 3 days before to 3 days after the maximum total symptom score, with the following conditions:

- If there are less than or equal to 3 days between maximum total symptom score and swab #1, the start of the sick period will be the day of the maximum total symptom score.
- If there are more than 3 days between the maximum total symptom score and swab #1, the start of the sick period must be at least 3 days after swab #1.
- If there are multiple days with maximum total symptom score, consider the one closest to the day of swab #2 as the center of the window.

The **well state** is defined by considering a window of Electronic Diary data around a negative RT-PCR test at swab #1, from 8 days before swab #1 up to 14 days before the maximum total symptom score. If there are less than 14 days between swab #1 and the maximum total symptom score, the well state window ends on the day of swab #1.

For participants who have a positive RT-PCR test at swab #1, the sick state definition is as follows:

The **sick state** is defined by considering a window of Electronic Diary data centered around the maximum total symptom score, from 3 days before to 3 days after the maximum total symptom score.

- If there are multiple days with maximum total symptom score, consider the one closest to the day of swab #1 as the center of the window.

For participants who have a negative RT-PCR test at both swab #1 and swab #2, the well state definition will remain as defined in Section 3, namely:

The **well state** is defined by considering an:

- Analysis time window from 8 days before swab #1 up to 8 days after swab #1
- Analysis time window of 8 days up to and including swab #2.

This well and sick data will serve as the input to the machine learning and deep learning analysis, and the models will be trained, validated and tested as described in [Section 4.2.5](#) and [Section 4.2.6](#).

4.5. Change from Baseline Analysis

This analysis will investigate change from individual-level baseline in participants who start the study as well (negative swab #1) and who become sick and symptomatic during the study

(positive swab #2). The individual-level baseline will be defined by up to the first three available days of that participant’s data within the first 7 days in the study.

The individual baseline will be subtracted from endpoint values that fall within the sick and well state windows as defined in [Section 3](#). This data will serve as the input to the machine learning models. The models will be trained, validated and tested as described in [Section 4.2.5](#). Deep learning modeling may also be performed on this data as described in [Section 4.2.6](#).

For the covariance model described in [Section 4.2.5](#), MFCC features will be used as the input to the model. The MFCCs matrices are not aligned in time across Electronic Diary sessions. Moreover, the difference between two positive definite matrices is not positive definite in general ⁵⁵. To account for this, MFCCs from the baseline will be mapped to the tangent space using methods described in [Section 4.2.5](#). Then the projected baseline vector will be subtracted from well or sick vectors in this tangent space.

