1.3. Schedule of Activities

The SoA table provides an overview of the protocol visits and procedures. Refer to the STUDY ASSESSMENTS AND PROCEDURES section of the protocol for detailed information on each procedure and assessment required for compliance with the protocol.

The investigator may schedule visits (unplanned visits) in addition to those listed in the SoA table, in order to conduct evaluations or assessments required to protect the well-being of the participant.

| Visit Identifier | Screening (Day 1) | Enrollmen t (Day 1 + 1 day) | Self-swab #1 (Day 2 + 6 days) | Self-swab #2 Symptomati c participants (Day 2 + 40 days) | Self-swab #2 Asymptomati c participants (Day 42 +1 days) | Extended electronic diary Only for virus positive participants ^f (Day 42 to 56) |
|--|-------------------|--------------------------------------|--|---|---|--|
| Informed consent | X | | | | | |
| Inclusion and exclusion criteria | X | | | | | |
| Access Electronic diary | | X | | | | |
| Demography | | X | | | | |
| Enrollment Questionnaire | | X | | | | |
| (includes self-reported medical | | | | | | |
| history) | | | | | | |
| Daily symptom and voice entry on the Electronic diary | | X | \rightarrow | \rightarrow | \rightarrow | \rightarrow |
| Obtain SARS-CoV- | | | Xa | X ^b | X° | |
| 2/influenzavirus/RSV nasal | | | | | | |
| self-swab | | | | | | |
| Enter date and time of self- | | | X | X | X | |
| swab when completed in | | | | | | |
| Electronic diary | | | | | | |

PFIZER CONFIDENTIAL

| Visit Identifier | Screening | Enrollmen | Self-swab | Self-swab #2 | Self-swab #2 | Extended electronic |
|--------------------------------|-----------|------------|---------------|---------------|---------------------------|---------------------------|
| | | t | #1 | Symptomati | Asymptomati | diary |
| | | | | С | С | Only for virus positive |
| | | | | participants | participants | participants ^f |
| | (Day 1) | | | | | |
| | | (Day 1 + 1 | (Day 2 + 6 | (Day 2 + 40 | (Day 42 +1 | (Day 42 to 56) |
| | | day) | days) | days) | days) | |
| Confirm no AE's 12 hours after | | | X | | X | |
| self-swab; enter date and time | | | | | | |
| in Electronic diary | | | | | | |
| End of Study Questionnaire | | | | | $\mathbf{X}^{\mathbf{d}}$ | Xe |
| Collect AEs and RRIs as | X | X | \rightarrow | \rightarrow | \rightarrow | \rightarrow |
| appropriate | | | | | | |

- a. Participant is required to perform self-swab #1 as soon as possible once they receive the collection kit.

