If the total symptom remains below 40% of the maximum total symptom score after swab #2, the end of the window will be the swab #2 day.

The **well state** is defined by considering a window of Electronic Diary data around a negative RT-PCR test at swab #1, from 8 days before swab #1 up to 14 days before a positive swab #2. If there are less than 14 days between swab #1 and swab #2, the well state window ends on the day of swab #1.

For Secondary Analysis Set A

The **well state** is defined by considering an:

- Analysis time window from 8 days before swab #1 up to 8 days after swab #1.
- Analysis time window of 8 days up to and including swab #2.

For Secondary Analysis Set B

The **sick state** is defined by considering an analysis time window of 3 days before and 3 days after swab #1, including swab #1 day.

CCI

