4.2.5. Classical Machine Learning

Using the reduced feature set from Section 4.2.3., classical machine learning algorithms will be trained to perform the binary classification of well versus sick states. Ensemble learning algorithms are the preferred method because they: typically generalize well, are very robust to overfitting, can be trained efficiently, require little hyper-parameter tuning to achieve competitive results, perform predictions quickly and can be easily packaged for deployment²⁰. The classical machine learning approach also lends itself to making understandable predictions. SHapley Additive exPlanations (SHAP)²¹ will be used to investigate the most successful models to determine to what degree each feature influences model output. The main classical machine learning models of interest include: Random Forest²²; Bagging²³; Extreme Gradient Boosting (XGBoost)²⁴; Light Gradient Boosting Machine (LGBM)²⁵; Support Vector Machine (SVM) Ensemble²⁶.

Additional modeling may include a combination of spectrograms (described in Section 4.2.4.) and voice features described in Section 4.2.2. The spectrogram averaged across time may be combined with the voice features and used as the input to the classical machine learning model. In early fusion, a classifier is trained on the combined set of voice features and averaged spectrograms. In late fusion, separate models are trained on averaged spectrograms and voice features, and the final prediction is the average of the output from the two models²⁷⁻²⁹.

In addition, covariance approach which quantifies the linear relationship between features will also be explored to perform the binary classification of well versus sick states. This

approach has been shown to be invariant to the linear transformation of the features³⁰. This invariance property might diminish the intersubject variability of the acoustic features and can also reduce any learning effects of the acoustic features over time on the model performance. The input data for this approach will be the MFCCs matrix, as described in [Section 4.2.4](#).

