4.2.5.1. Classical Machine Learning Model Training and Testing

The data will be randomly divided into two sets by subject: training (e.g., 80% of subjects) and test set (e.g., 20% of subjects). Repeated stratified k-fold cross validation (on the subject level) on the training data will be used to evaluate performance, as it provides confidence in the resulting performance values. Both k (number of folds) and n (number of repetitions) will be chosen based on the final sample size. The test set will be a hold-out test set until model training and validation is complete.

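### In the change-from-baseline algorithm the baseline days also count as well samples, which inflates AUC and specificity of the preferred non-linear classifiers

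*SAP*

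**What the plan says.** All sections cited are in the algorithm development plan (SAP Appendix A) unless marked otherwise.

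- **Baseline.** Section 4.5: "The individual-level baseline will be defined by up to the first three available days of that" participant's data, within the first 7 study days.
- **Use of the baseline.** Section 4.5: "The individual baseline will be subtracted from endpoint values that fall within the sick and well state windows as defined in" Section 3.
- **Well window, Primary Analysis Set.** Section 3 sets it "from 8 days before swab #1 up to 14 days before a positive swab #2", with the rider: "If there are less than 14 days between swab #1 and swab #2, the well state window ends on the day of swab #1".
- **Well windows, Secondary Analysis Set A (negative at both swabs).** Section 3 gives two: 8 days either side of swab #1, and "Analysis time window of 8 days up to and including swab #2". Section 4.6 uses this set to check the false positive rate of the Section 4.5 model.
- **Swab #1 timing.** Protocol Section 1.3: "Self-swab #1 (Day 2 + 6 days", which by the note to that table means Day 2 to Day 8.
- **Classifier.** Section 4.2.5: "Ensemble learning algorithms are the preferred method because they: typically generalize well".
- **Validation.** Section 4.2.5.1: "The data will be randomly divided into two sets by subject", for example 80% training and 20% test.
- **Targets.** Section 4.1: observed sensitivity of at least 70%, minimum specificity 60%.

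No text removes the baseline days from the well samples or mentions the overlap.

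**The concern.** A day that helped to form the baseline lies closer to that baseline than any other day of the same person, whether or not anyone falls ill. If such days appear among the well samples and hardly ever among the sick samples, closeness to baseline becomes a marker for the well label that has nothing to do with infection.

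The two safeguards do not remove this. Splitting by subject leaves the same construction in place for the held-out subjects. The test on double-negative participants uses a set whose first well window also covers the baseline days.

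At stake are the AUC and specificity reported for the Section 4.5 model, and its comparison with the models of Sections 4.2.5, 4.2.6 and 4.4, which subtract no such baseline. The gain would not carry over to use, where the day being scored is not part of its own baseline.

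**Working it through.** **1. The plan's own figures.** The plan gives no AUC or specificity for Section 4.5, so there is nothing to reproduce on this point. Its sensitivity figures in Section 4.1 do reproduce. The normal approximation with 100 cases gives 0.021, 0.876 and 0.994 (stated 0.02, 0.88, 0.99), and 1.96 × √(0.21/100) = 8.98%. They do not bear on this issue.

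**2. Overlap of baseline and well window.** Swab #1 on Day 2 to 8 opens the well window between Day 2 − 8 = −6 and Day 8 − 8 = 0, so it always covers Day 1.

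- Example, long gap: swab #1 on Day 5, swab #2 on Day 30. The well window is Days 1–16. With a full diary, 3 of 16 well days are baseline days.
- Example, short gap: swab #1 on Day 3, swab #2 on Day 12. The gap is 9 days, so the window is Days 1–3 and every well day is a baseline day.

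Weighting all allowed swab-day pairs equally, 98%, 96% and 94% of baseline days fall in the well window at 100%, 80% and 60% diary completion.

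In 60,000 simulated schedules per setting (swab #1 uniform on Day 2–8, swab #2 uniform up to Day 42, sick window from 2 days before to 6 days after swab #2):

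| Diary completion | Baseline days as share of pooled well samples | Participants whose well window holds only baseline days |
|---|---|---|
| 100% | 24% | 11% |
| 80% | 29% | 17% |
| 60% | 36% | 26% |

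Baseline days are under 1% of sick samples.

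**3. Variance, taking the baseline as a mean of m days with day-to-day variance σ².** For independent days:

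- baseline day: σ²(1 − 1/m) = 0.67σ² for m = 3;
- any other day: σ²(1 + 1/m) = 1.33σ² for m = 3.

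Both have mean zero, so only the spread differs. With m = 1, which the rule allows, the change is exactly 0.

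For AR(1) correlation 0.5 and three consecutive baseline days, the baseline mean has variance (3 + 2 × (0.5 + 0.5) + 2 × 0.25)/9 = 0.611σ². Then:

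- Days 1 and 3: 1 + 0.611 − 2 × (1 + 0.5 + 0.25)/3 = 0.444;
- Day 2: 1 + 0.611 − 2 × (0.5 + 1 + 0.5)/3 = 0.278;
- a distant day: 1.611.

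**4. Separability with no illness effect.** Using squared distance from baseline, the AUC of baseline days against sick days (m = 3, independent features) is 0.61, 0.77, 0.86, 0.94 and 0.99 for 1, 5, 10, 20 and 50 features. If baseline days are a share f of the well samples, overall AUC = 0.5 + f(AUC_b − 0.5). For 20 features and f = 0.3 this is 0.5 + 0.3 × 0.44 = 0.63.

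**5. Simulated hold-out, no illness effect.** 100 cases, 80/20 split by subject, random forest, independent days or AR(1) = 0.5 with inter-feature correlation 0.3; 10–12 runs per setting, SE of AUC 0.006–0.016:

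| Features | AUC | Specificity at 70% sensitivity |
|---|---|---|
| 5 | 0.51–0.61 | 33–48% |
| 10 (independent days only) | 0.55–0.58 | 37–43% |
| 40 | 0.59–0.68 | 44–56% |
| Baseline days excluded | 0.49–0.52 | 28–34% |
| No information | 0.50 | 30% |

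Logistic regression stays at AUC 0.48–0.51.

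A separately built simulation (six scenarios, 25 runs each) gave AUC 0.54–0.65 and specificity 35–52% as planned, against 0.49–0.51 and 29–31% with baseline days excluded. In its 20-feature case at 80% completion, specificity was 79% on baseline days and 30% on other well days. With a baseline share of 0.32, that is 0.32 × 0.79 + 0.68 × 0.30 = 0.46, so the whole gain comes from the baseline days.

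**6. Secondary Analysis Set A, no illness effect.** Null specificity is 32–57% in the swab #1 window, 28–34% in the swab #2 window and 31–47% pooled.

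**7. With a real signal.** 20 independent features, 80% completion, 16 runs; specificity at 70% sensitivity:

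| Mean shift on sick days | As planned | Excluded |
|---|---|---|
| none | 43% | 31% |
| 0.15 SD per feature | 55% | 44% |
| 0.20 SD per feature | 63% | 55% |

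The SE is about 1–1.5 points. In the last row the planned model reaches only 53% on well days that are not baseline days.

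**The case against.** The mechanism is hard to dispute; the case on the other side concerns size, reach and remedy.

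- **The inflation fades with signal.** This stands. In a further set of runs, whose signal was set up separately so that levels should not be compared with the table above, specificity was 58.5% against 49.4% at a 0.4 SD shift, and 78.7% against 75.2% at 0.8 SD (SE about 2 points). The gap falls from 9.1 to 3.5 points.
- **Unstated modelling assumptions.** The plan never says that the baseline is a mean, and the main runs give everyone the same day-to-day SD. When the SD varied by participant and feature, null AUC with 20 features and independent days fell to 0.550 (0.512 excluded); with AR(1) as well it was 0.632. The effect is reduced, not removed.
- **Few features.** With 5 features the low end (AUC 0.51) cannot be told from no effect, and Section 4.2.3 plans heavy feature elimination. This stands: the direction is certain, the size is not.
- **Limited consequence.** The formal success criterion is sensitivity, and no rule picks Section 4.5 over the other models. True, but specificity has a stated minimum, and the 0.20 SD case shows a model passing 60% because of baseline days.
- **Already checked in Set A.** Only in part. The swab #2 window is essentially clean, but the plan does not report it separately.
- **Exclusion may be incomplete under autocorrelation.** Days just after the baseline stay closer to it (variance about 1.03 against 1.61). One set of runs left AUC at 0.530 (SE 0.008) after exclusion; a repeat gave 0.501, so this was not confirmed.

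**Conclusion.** The concern holds. As written, Section 4.5 biases the AUC and specificity of non-linear classifiers upward in training, in the hold-out and in the swab #1 window of Secondary Analysis Set A. Linear classifiers and the models of Sections 4.2.5, 4.2.6 and 4.4 are unaffected.

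With no illness effect, the inflation ranges from almost nothing with 5 features to an AUC of 0.68 and a specificity of 56% with 40. The artefact alone does not reach 60% specificity at 70% sensitivity, but it can carry a weak model over that line.

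The size depends on assumptions that the documents do not supply: swab timing, length of the sick window, diary completion, number and correlation of retained features, Gaussian noise, and the baseline taken as a mean. The overlap is normal rather than universal: with a very early swab #1 and a short gap, Day 3 can fall outside the well window, and a swab #1 taken well after Day 8 would also break the pattern.

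**What to change.** Add two sentences to the algorithm development plan:

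1. In Section 4.5, and whenever its model is tested on Secondary Analysis Set A, exclude the days that form the individual baseline from the well samples. Participants with no other well days contribute sick days only.
2. Report Set A specificity separately for the swab #1 window and the swab #2 window.

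The exclusion is needed in Set A as well as in training. In the AR(1) runs, a model fitted without baseline days still showed 66% specificity on the Set A baseline days and 39% pooled, against 32% in the swab #2 window. It would also help to state whether the baseline is a mean.

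No new data are needed. The cost is about 24–36% fewer well samples, and none at all for roughly 11–26% of cases, which weakens the within-person contrast for them. If that loss is unwelcome, a leave-one-day-out baseline using the same number of days for every sample is an alternative.

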4.6. Further Model Testing

The best-performing output models from the classical machine learning ([Section 4.2.5](#).) deep learning ([Section 4.2.6](#).), fusion method ([Sections 4.3](#).) and well vs. sick analysis with sick state definition centered around maximum symptom score ([Section 4.4](#).) will be tested on data of:

- (a) Negative cases to get an estimate of the false positive rate.
- (b) Symptomatic positive participants at swab #1 as an additional dataset for testing the sensitivity rate of the models.

CCI [REDACTED]

For the Change From Baseline Analysis ([Section 4.5](#).), the best performing model will be tested on participants who are negative at both swab #1 and swab #2 to investigate the false positive rate of this approach.

CCI [REDACTED]

CCI

CCI

4.8. Methods to Manage Missing Data

All summaries and analyses will be based on observed data and missing data imputation is not planned. Inadequate compliance data will be used as recorded.

5. ANALYSES AND SUMMARIES

5.1. Classification of Well and Sick States using Classical Machine Learning Models

- Analysis Set: Participants in Primary Analysis Set ([Section 3](#)).
- Statistical Method: Classical machine learning modeling will be performed as described in [Section 4.2.5](#). The best performing model will be selected based on performance metrics listed in [Section 4.2.5.2](#).

- Summaries:

Using the output of the best performing model described in [Section 4.2.5.3](#), the following results will be generated for the specified analysis set (data permitting):

- Listing of the features used in the final model
- Summary statistics of the performance measures listed in [Section 4.2.5.2](#). (mean and standard deviation) for classification of sick and well states for the validation set. Results will be presented in a table.
- The confusion matrix for the test set will be tabulated and a listing of the performance measures provided.

5.2. Classification of Well and Sick States Using Deep Learning Models

- Analysis Set: Participants in Primary Analysis Set if deemed appropriate by data.

- Statistical Method: Deep learning modeling will be performed as described in [Section 4.2.6](#). The best performing model will be selected based on performance metrics listed in [Section 4.2.6.4](#).

- Summaries:

Using the output of the best performing model described in [Section 4.2.6.5](#)., the following results will be generated for the specified analysis set (data permitting):

- Listings of the specifications of the spectrograms and mel-spectrograms used for the final deep learning model ([Section 4.2.4](#).)
- Summary statistics of the performance measures listed in [Section 4.2.6.4](#). (mean and standard deviation) for classification of sick and well states for the validation set. Results will be presented in a table.
- The confusion matrix for the test set will be tabulated and a listing of the performance measures provided.

If a fusion model is deemed appropriate by data (as described in [Section 4.3](#).), the following will be generated:

- Listings of the voice features ([Section 4.2.2](#).) and specifications of the spectrograms and mel-spectrograms used for the final model ([Section 4.2.4](#).)
- Summary statistics of the performance measures listed in [Section 4.2.6.4](#). (mean and standard deviation) for classification of sick and well states for the validation set. Results will be presented in a table.
- The confusion matrix for the test set will be tabulated and a listing of the performance measures provided.

5.3. Well vs. Sick Analysis with Sick State Definition Centered Around Maximum Total Symptom Score

- Analysis Set: Participants in Primary Analysis Set ([Section 3](#)) if deemed appropriate by data.
- Statistical Method: Listed in [Section 4.4](#).
- Summaries:

Using the output of the best performing classical machine learning ([Section 4.2.5](#).), deep learning ([Section 4.2.6](#).) or fusion method ([Section 4.3](#).), the following results will be generated for the specified analysis set (data permitting):

- Listing of the features used in the final classical machine learning model and/or Listings of the specifications of the spectrograms and mel-spectrograms used for the final deep learning model ([Section 4.2.4](#).)
- Summary statistics of the performance measures listed in [Section 4.2.5.2](#). (mean and standard deviation) for classification of sick and well states for the validation set. Results will be presented in a table.
- The confusion matrix for the test set will be tabulated and a listing of the performance measures provided.

